- Type: Mode of exercise will vary based on participant limitations and choice, including activities such as walking, biking, elliptical machine, and swimming, with individual mode being consistently maintained whenever possible throughout the duration of the study. Cycling will be suggested as the primary mode, but another mode will be selected if cycling is not feasible. If limitations arise for the participant during familiarization and throughout the study (i.e. discomfort, inability to increase heart rate), training mode will be modified, and noted, to inform feasibility components (Aim 1).
- Intensity: Individualized training intensity for each participant will be established from baseline cardiovascular fitness (VO2peak) testing. Baseline maximal oxygen consumption testing and maximum workload will be used to determine the intensity of each exercise bout (90% of maximum heart rate obtained during testing).
- Session: Each training session will consist of a 3-5 minute warm-up, followed by 10 repetitions of 1-minute bouts at individualized training intensity with 1-minute rest periods. We anticipate that most participants in this study will be able to complete all 10 1-minute bouts during the first session, based on our prior experience of HIIT in people with other diseases who have low levels of physical activity at baseline. Individuals who are

unable to achieve this protocol in initial sessions will be encouraged to complete all 10 bouts for as long as possible each bout. If they cannot finish the entire minute, the 1-minute rest period will begin as soon as they stop, followed by the next bout. Intensity will be re-established and adjusted following the 6-week testing. Sessions will take place twice per week, with at least 24 hours in between training sessions.

Structured Interview. A structured one-on-one interview will occur with participants after completion of the HIIT program. The interview will be used to learn about barriers and concerns they experienced with regard to the current training protocol; preference of exercise mode and instruction; and opinions on what information participants would find helpful to transition to an at-home and or independent program. While we do not intend to formally analyze the interview responses, we do anticipate that they will be useful for refining our intervention program for inclusion and development of a home-based component for future trials.

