Three participants per month are expected to be enrolled with at least 80% retention during the study period. As part of Aim 1, adherence to and tolerability of HIIT, acceptability, and recruitment and retention rates of patients through 6- and 12-week assessments will be determined. This will be determined as the percent of participants that screen into the study versus those approached and the percent of participants retained at the 6- and 12-week post-tests. Frequency and reasons for initial refusal, ineligibility, and drop out will be collected. Adherence and tolerability will be evaluated based on number of sessions attended/completed, modifications, such as change in mode; number of training days per week; recovery days needed between sessions to complete training, and severity of pain on a scale of 0-10 (no pain-extreme pain) during and after exercise as a measure of tolerability. If the HIIT intervention is shown to be well-tolerated and promising, results of this preliminary study will lay the foundation for a large randomized controlled trial to establish the efficacy of HIIT as a revolutionary approach for enhancing the rehabilitation and management of knee OA.

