# **Eligibility Criteria**

All participants must meet the following criteria:

- Between the ages of 40 and 75 years old
- Body mass index of 18.5-50 kg/m^2
- Exhibits symptomatic knee OA, defined as a diagnosis of knee OA, as identified from UNC electronic medical records, and current knee symptoms in at least one knee, having a minimum score of 6 out of 20 on the Western Ontario and McMasters Universities Osteoarthritis Index (WOMAC) pain subscale.

Potential participants meeting any of the following criteria (based on the electronic medical record or in laboratory screening) will be excluded if:

- Individuals diagnosed with a cardiovascular condition restricting exercise
- Individuals currently meeting Department of Health and Human Services Guidelines for physical Activity (≥ 150 minutes per week)
- Individuals currently doing HIIT
- Individuals currently participating in physical therapy for knee OA
- Individuals currently participating in another OA intervention study
- Received a corticosteroid or hyaluronic acid intra-articular injection involved in the knee in the previous 3 weeks or scheduled for during the intervention
- Diagnosis of gout in the knee
- Diagnosis of Rheumatoid arthritis
- Diagnosis of Fibromyalgia
- Other systemic rheumatic disease
- Severe dementia or other memory loss

- Active diagnosis of psychosis or uncontrolled substance abuse disorder
- Hospitalization for a stroke, heart attack, or heart failure, or had surgery for blocked arteries in the past 3 months
- Total joint replacement knee surgery, other knee surgery, meniscus tear, or ACL tear in the past 6 months
- On a waiting list for total joint replacement
- Severely impaired hearing or speech
- Pregnant or planning to become pregnant while enrolled in the study
- Inability to speak English
- Serious or terminal illness as indicated by referral to hospice or palliative care
- Nursing home residence
- Inability to ride a stationary bike
- Any other health problems that would prohibit safe participation in the study.

Use and changes of medications for OA will be monitored and recorded during the study but will not be a reason for exclusion. Participants will be withdrawn if they develop any new health problems or other events that would either a) make participation in the study intervention or measures unsafe or b) confound study outcomes. These largely mirror study exclusion criteria and are as follows:

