# Participant Evaluations and Follow-up

### **Timeline and Visit Schedule**

The current study consists of 27 total visits: 3 testing visits and 24 training sessions. All visits will take place at the Applied Physiology Laboratory and/or the Student Recreation Center. The three testing visits will consist of assessments of physical function, cardiorespiratory fitness, body composition, balance, symptoms, and muscular strength. These visits will occur at baseline, 6-weeks, and 12 weeks. The HIIT intervention will occur over the course of 24 separate training sessions, occurring two times per week for two 6-week sessions.

Week	Visit	Testing	Training	Measures Collected
	#			
0	1	X		
 
Physical function: 40 m fast-paced walk test, 30-s chairstand test, a stair-climb test, and Timed Up and Go Test
 
Knee OA Symptomatic Burden: WOMAC
 
Balance: single leg stance and side-by-side, semi-tandem, and tandem tests
 
Muscle Strength. isokinetic dynamometer for power at 60 degrees per second and for strength at 60 degrees of knee flexion.
 
Cardiorespiratory fitness: peak oxygen consumption (VO2peak)
 

				Body composition: DXA for fat mass, lean body mass, and visceral fat
1-5	2-11		X	
 
Heart rate: chest strap heart rate monitors to identify heart rate and intensity during each training bout
 
Ratings of perceived exertion: Borg perceived exertion scale
 
Severity of pain: visual analog scale of 0-10 (no pain-extreme pain) during and after exercise
 
Training bouts completed
 
Mode of exercise
 
Exercise enjoyment
 

6	12	X		
 
Physical function: 40 m fast-paced walk test, 30-s chairstand test, a stair-climb test, and Timed Up and Go Test
 
Knee OA Symptomatic Burden: WOMAC
 
Balance: single leg stance and side-by-side, semi-tandem, and tandem tests
 
Muscle Strength. isokinetic dynamometer for power at 60 degrees per second and for strength at 60 degrees of knee flexion.
 
Cardiorespiratory fitness: peak oxygen consumption (VO2peak)
 
Body composition: DXA for fat mass, lean body mass, and visceral fat
 

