7-12	13-26		X	
 
Heart rate: chest strap heart rate monitors to identify heart rate and intensity during each training bout
 
Ratings of perceived exertion: Borg perceived exertion scale
 
Severity of pain: visual analog scale of 0-10 (no pain-extreme pain) during and after exercise
 
Training bouts completed
 
Mode of exercise
 
Exercise enjoyment
 

13	27	X		
 
Physical function
 
Knee OA Symptomatic Burden
 
Balance
 
Muscle Strength
 
Cardiorespiratory fitness
 
Body composition
 
Structured interview: barriers and concerns experienced with current training protocol; preference of exercise mode and instruction; opinions on what information participants would find helpful to transition to an at-home and or independent program
 

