# Aim 2 Analyses

All available data from all enrolled participants, regardless of extent of adherence to HIIT, will be descriptively summarized in tables and graphs. Longitudinal models will be fit for all outcomes (physical function, knee OA symptomatic burden, balance, muscle strength, cardiorespiratory fitness, and body composition) using all available data with linear mixed models. Mixed models allow for inclusion of all observed outcome data for each participant under the assumption that any missing data are missing at random. No missing data will be imputed. Separate models will be fit for each outcome with no adjustments for multiple comparisons since this is an exploratory proof-of-concept study; however, data from all outcomes assessed will be reported regardless of "significance". For each model, fixed effects will include visit, gender, baseline BMI, age, and severity of baseline OA symptoms. Additionally, if at least 10% of participants are not using prescribed pain medications at each time point, we will include dichotomous use of pain medication as a time-dependent fixed effect. Each model will also include random participant effects to account for correlation between repeated outcome measurements. For each outcome, we will use the model to estimate the mean change from baseline to each follow-up visit along with 95% confidence intervals.

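### The barriers interview and the later outcome assessments are not planned for participants who stop or are withdrawn, and the Aim 2 model has no stated check on its missing-at-random assumption

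*Combined protocol and SAP*

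**What the plan says.** **Interview.** The Structured Interview paragraph says "A structured one-on-one interview will occur with participants after completion of the HIIT program", and the text under Determining Participant Satisfaction repeats this. In the visit table the item "Structured interview: barriers and concerns experienced with current training protocol" appears only at visit 27, the last one. The interview also covers preferred exercise mode and instruction, and what would help people move to a home programme. It is meant to refine the intervention for later trials, but it is not an endpoint: "While we do not intend to formally analyze the interview responses".

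**Visits.** Timeline and Visit Schedule states: "The current study consists of 27 total visits: 3 testing visits and 24 training sessions". Testing is at baseline, mid-programme and the end. No early-termination or exit visit is listed.

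**Withdrawal.** Under Eligibility Criteria, "Participants will be withdrawn if they develop any new health problems or other events that would either" make participation unsafe or confound the outcomes. The list that follows includes new rheumatic diagnoses, joint surgery and ACL tear. No assessment at or after withdrawal is described.

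**What is kept from those who leave.** Reasons for drop-out are collected. Enjoyment, pain, bouts completed and exercise mode are recorded at training sessions, and the Aim 1 analysis covers all participants.

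**Analysis.** Aim 2 Analyses uses "All available data from all enrolled participants, regardless of extent of adherence to HIIT", with linear mixed models that assume missing at random. There is no imputation, and no sensitivity analysis is stated.

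**Expected loss.** The retention section expects "at least 80% retention during the study period", while Power and Sample Size assumes at most 10% loss at 12 weeks.

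**The concern.** Feasibility and acceptability are Aim 1, and the interview is the only place where participants are asked in depth what stood in their way. Those who stop because of pain, time or dislike have much to say on this, and the plan does not schedule them to be asked. A recorded drop-out reason is much narrower than the interview. Session enjoyment and pain end when attendance ends, so summaries for the later training days describe only those still attending.

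For Aim 2, someone who leaves before week 6 has only baseline data, and someone who leaves after week 6 has no final value. If leaving is linked to a knee that worsened after the last observed visit, the data are not missing at random. The model's mean change would then lean towards improvement. Both primary outcome domains, performance-based function and symptomatic burden (pain), are exposed. The results are intended to support a larger randomised trial.

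**Working it through.** **1. The plan's own figure.** Inputs from Power and Sample Size: SD 10 s, correlation 0.6, 30 enrolled, 10% loss, 5 s mean change, two-sided 5% test.
- SD of change = 10 × √(2 × (1 − 0.6)) = 8.94 s.
- n = 30 × 0.90 = 27.
- Power by normal approximation: Φ(5/8.94 × √27 − 1.96) = 82.8%. By noncentral t: 79.8%. The stated 80% is reproduced to within rounding.
- At 20% loss, n = 24 and power is 78.2% (normal) or 74.6% (t).

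**2. How many people are concerned.** 30 × 10% = 3, from the sample-size section. 30 × 20% = 6, from the retention floor. Both are limits given by the plan, not predictions.

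**3. What is available for someone who leaves.**

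| Information | Leaves before week 6 | Leaves after week 6 |
|---|---|---|
| Drop-out reason | yes | yes |
| Session enjoyment and pain | up to last session | up to last session |
| Week-6 outcomes | not planned | yes |
| Week-12 outcomes | not planned | not planned |
| Barriers interview | not planned | not planned |

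**4. Possible size for the walk test.** Assumptions, not taken from the documents: completers improve by 5 s (the plan's target difference), drop-outs' true mean improvement is 2.5, 0 or −5 s, and the model recovers none of that difference.

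All-enrolled mean = (1 − loss) × 5 + loss × drop-out change. Overstatement = 5 − that mean = loss × (5 − drop-out change).

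| Drop-outs' true improvement | 10% loss: mean / overstatement | 20% loss: mean / overstatement |
|---|---|---|
| 2.5 s | 4.75 / 0.25 s | 4.5 / 0.5 s |
| 0 s | 4.5 / 0.5 s | 4.0 / 1.0 s |
| −5 s (worse) | 4.0 / 1.0 s | 3.0 / 2.0 s |

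Relative to 5 s this is 5–20% at 10% loss and 10–40% at 20% loss.

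**5. Set against sampling error.** The half-width of a 95% paired t interval is t × 8.94/√n. This gives 3.54 s at n = 27 and 3.78 s at n = 24. The possible bias is smaller than the random uncertainty, but it runs in one direction under these scenarios and the interval does not reflect it.

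**The case against.** The other side has a good deal to say.

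- **Completing is not benefiting.** A reader might infer that acceptability and change will be learned only from people for whom the programme worked. The documents do not support that. A participant who reaches the last visit unimproved or in pain is still tested and interviewed, and poor adherers who stay are included in the analysis.
- **Aim 1 does not rest on the interview.** Attendance, session enjoyment and pain, changes of mode and drop-out reasons come from everyone while they take part. The interview is not formally analysed, so its gap affects programme refinement rather than a reported Aim 1 statistic.
- **Leavers do inform the model.** Their baseline and any week-6 values enter the likelihood. Only what happens after the last observed visit is lost, and the missing-at-random assumption is stated openly.
- **No contradiction.** A reader might set the withdrawal rule against the Aim 2 analysis set. That section promises all available data whatever the adherence. It does not promise data after withdrawal.
- **The figures depend on assumed drop-out outcomes**, and the study is small, single-arm and exploratory.
- **The flow diagram is not shown** and might contain an exit step.

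All of this stands, and it limits the point. It does not remove the gap: none of the retained data covers the interview's questions for those who stopped, none can show later worsening, and openly stating an assumption does not test it.

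**Conclusion.** The point holds as a gap in planned data collection and in sensitivity analysis. In the readable text, neither the barriers interview nor the remaining outcome assessments are planned for participants who stop or are withdrawn. About 3 to 6 of 30 are concerned. For the walk test, the mean improvement would be overstated by about 0.25–1.0 s at 10% loss and 0.5–2.0 s at 20% loss. This rests on a 5 s improvement in completers, drop-outs between 2.5 s better and 5 s worse, and no recovery of the difference by the model. Where week-6 values already show a poorer course, the model would recover part of it and the overstatement would be smaller.

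This does not invalidate the Aim 1 summaries or the choice of mixed model. It is a cheap improvement to a feasibility study whose purpose is to inform the next trial.

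**What to change.** 1. **Interview.** In the Structured Interview paragraph, under Determining Participant Satisfaction and in the visit table, reword the timing to completion or discontinuation. Offer the interview by telephone to anyone who stops.
2. **Follow-up.** Next to the withdrawal rules, state that stopping training does not end follow-up unless consent is withdrawn. Collect KOOS/WOMAC, which is a questionnaire, and adverse events remotely at the original week-6 and week-12 dates. The clinical rules on when training stops are left as they are.
3. **Analysis.** Remote questionnaires cannot recover performance tests, so add a delta-shift (missing-not-at-random) sensitivity analysis for the walk test to Aim 2 Analyses. A simple form reduces the model's mean improvement at week 12 by the proportion missing × delta, with delta running from 2.5 s to 10 s (the gaps 5 − 2.5 and 5 − (−5) used above). This needs no imputation.
4. **Expected loss.** Reconcile the 10% loss assumption with the 80% retention floor.

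The cost is a few calls and questionnaires for roughly 3 to 6 people, some protocol wording, a short added analysis and an IRB amendment. Some who stop will decline, so the gap will shrink rather than close.

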# **Study Flow Diagram**

[figure not shown]

# **Study Personnel Organization**

# **Participant Recruitment and Retention**

This study will be conducted in the Applied Physiology Lab within the Department of Exercise and Sport Science and Campus Recreation Center at the University of North Carolina at Chapel Hill. Recruitment will take place at the University of North Carolina Hospital, the Thurston Arthritis Research Center, and the Department of Family Medicine.

#### Recruitment

All relevant members of the research team will be instructed on the procedures for recruitment of study participants. We will use methods that are currently successful for recruiting individuals with knee OA for exercise interventions at UNC. In the first 9 months of enrollment for a previous study, "Physical Therapy vs. Internet-Based Exercise Training for Patients with Knee Osteoarthritis" (PI [name], co-I [name]), 40 218 people with knee OA have been enrolled in the UNC area, surrounding communities, and Smithfield, North Carolina using inclusion/exclusion criteria and methods similar to the current study (total needed 350). In a similar manner to that study, patients will be initially identified from UNC medical records based on ICD-10 codes; individuals who meet initial eligibility criteria based on the medical record will be mailed introductory letters. Additionally, flyers and brochures will be posted at UNC and the surrounding community, and UNC healthcare providers in rheumatology, orthopedics, primary care, and physical therapy will provide brochures to patients. Individuals interested in the study will be screened for eligibility criteria via telephone. Individuals who meet eligibility criteria and are interested in participating will meet a study team member to complete informed consent and inclusion criteria. All potential patients will undergo a 12-lead electrocardiogram and will be cleared to participate following medical history review from Drs. [name] and [name]. Following clearance, baseline testing will occur.

We will enroll patients who have sought care for knee osteoarthritis from the University of North Carolina at Chapel Hill (UNC), a large not-for-profit healthcare system that provides both primary and specialty care. Over 800,000 people receive outpatient care at UNC clinics annually. Based on the patient populations in our enrollment site and experience from our previous studies, there will be an ample number of patients eligible for the proposed study. Our estimate of potentially eligible patients at UNC is based on the number of outpatients age 55, n=119,517, and the prevalence of symptomatic knee OA in this age group (about 12%). Based on these numbers, we estimate there will be a total of over 14,000 patients with knee OA at UNC. Given this large number, we will be able to focus recruitment on patients who live within reasonable driving distance to study enrollment sites and physical therapy clinics (which still encompasses a range of geographic regions in terms of urban/rural status).

#### Inclusion of Women and Minorities

The sample in the current study will be comprised of approximately 50% women. The University of North Carolina community is comprised of 58.1% of females as reported by the U.S. News and World Report in 2015. Knee osteoarthritis is highly prevalent among both men and women, and women have a higher risk of knee osteoarthritis than men. Therefore, we do not anticipate problems recruiting women into the proposed study.

All races and sexes will be included in the current study. The racial/ethnic composition of the current study is expected to be representative of the diversity of the United States and greatly reflect the composition of the Chapel Hill, North Carolina area. According to the 2010 Census Bureau, the Chapel Hill, North Carolina area is comprised of 72.76% white, 9.66% African American, 0.31% Native American, 11.86% Asian, 0.02% Pacific Islander, while 2.68% are considered other and 2.70% consider themselves as two or more races. There was

6.36% of the population that was considered Hispanic or Latino. We will recruit minority races/ ethnicities aggressively to ensure the study sample is representative of the general population (See Targeted/ Planned Enrollment Table).

# **Targeted/Planned Enrollment Table**

Targeted/Planned Enrollment: Number of Subjects						
Ethnic Categories		Sex				
C	Males	Females	Total			
Hispanic or Latino	2	2	4			
Not Hispanic or Latino	13	13	26			
Ethnic Categories: Total of All Subjects	15	15	30			
Racial Categories Native American	1 1	1	2			
Asian	1	1	2			
Pacific Islander	1	1	2			
African American	1	1	2			
White	10	10	20			
Two or More Races	1	1	2			
Racial Categories: Total of All Subjects	15	15	30			

# **Participant Retention Plan**

All relevant members of the research team will be responsible for participant retention. The following section details the procedures for participant retention, which will be carried out by the Research Assistant, the Study Coordinator and the Principal Investigator throughout the entire duration of the study.

Role of the Research Assistant, Study Coordinator and the Principal Investigator

The Research Assistant, Study Coordinator and the Principal Investigator will be responsible for ensuring participant recruitment and retention through 1) informing the research team of appropriate recruiting and retention procedures 2) determining the success of current strategies to recruit and retain study participants, and 3) evaluating and improving participant recruitment and retention strategies throughout the duration of the study. The following major principles will be implemented throughout the study in order to maximize participant retention.

